4.1.2 SECONDARY ENDPOINTS

1. Secondary measures of wound healing efficacy will be assessed through week 12 by determining:
 - a. Time to complete wound closure as determined by wound image planimetry using the Silhouette Star camera system by Aranz®.
 - b. Wound characteristics including granulation tissue quality and presence/quantity of exudate as determined by standardized clinician evaluation.
 - c. Incidence of bridging to definitive closure such as graft, flap (when bridging is the goal of treatment), or transition to cellular therapy as determined by investigator.
2. Effect of treatment on patient-reported quality of life will be assessed by Visual Analog Scale (VAS), Wound Quality of Life (W-QOL), and Katz ADL health-related quality of life surveys at healing or at 12 weeks if the wound remains unhealed.
3. Complete wound management will be assessed through week 12 by recording the following on a standardized questionnaire:
 - a. Method of application of Cytal®/MicroMatrix® and how the product is secured (e.g. sutures, steri-strips).
 - b. Adjunctive treatments and dressings (e.g. debridement, offloading, negative pressure wound therapy, hyperbaric oxygen).
4. Number and type of wound-related adverse events through week 12 as recorded on adverse event case report forms.

4.1.3 TERTIARY ENDPOINTS

1. Costs of treatment and patient work status will be assessed through week 12 by the following:
 - a. Direct wound-related costs will be calculated and stratified by product and care cost.
 - b. Current employment status and return to work status will be recorded and frequency of changes will be assessed.
 - c. Measure frequency of wound specific AEs and SAEs.
2. Wound Pathology will be assessed through week 12 by the following:
 - a. Effect of treatment with Cytal® with or without MicroMatrix® on pro-inflammatory and anti-inflammatory macrophage biomarkers, vascularization, and fibrosis in wound tissue biopsies will be assessed through quantitative image analysis for the following stains:

- i. CD86 and CD163 immunostains to quantify pro-inflammatory M1 and anti-inflammatory M2 macrophage phenotypes.
 - ii. CD31 immunostain to quantify vascularization.
 - iii. Masson's trichrome to quantify fibrosis.
- b. Pathologists' findings over the course of treatment will be assessed by quantification of standardized pathologists' findings in wound pathology reports based on Hematoxylin and Eosin staining.

5. STUDY ENROLLMENT AND WITHDRAWAL

5.1 PARTICIPANT INCLUSION CRITERIA

In order to be eligible to participate in this study, an individual must meet all of the following criteria:

1. Subject has at least one wound that the treating physician determines may be treated with Cytal® with or without MicroMatrix®.
2. Subject is ≥ 22 years of age.
3. Subject is willing and able to adhere to protocol requirements and agrees to participate in the study program and comply with the study follow-up regimen.
4. Subject or legal representative is willing to provide informed consent.
5. For females of reproductive potential, confirmed negative pregnancy test at enrollment.

5.2 PARTICIPANT EXCLUSION CRITERIA

An individual who meets any of the following criteria will be excluded from participation in this study:

1. Allergy or hypersensitivity to materials in porcine-based study products (per subject report) or personal preference.
2. Subject report of concurrent participation in another clinical trial that involves an investigational drug or device that would interfere with this study.
3. The subject has any physical or psychiatric condition that, in the Investigator's opinion, would warrant exclusion from the study or prevent the subject from completing the study.
4. The subject's wound shows evidence of infection as determined by the Principal Investigator (which may be indicated by presence of: elevated WBC, pus, moderate or greater discharge, abnormal odor, or acute osteomyelitis).
5. Wound with exposed organs or hardware.
6. Wound with burn etiology.

5.3 STRATEGIES FOR RECRUITMENT AND RETENTION

80 subjects (maximum of 100 enrolled) are expected to complete the trial after an approximate 20% dropout/withdrawal rate. The enrollment process will take place over a 12 month period

between June 2018 and May 2019, with all subjects expected to have completed the study by May 2020. All eligible patients will be selected for participation from within NYU Winthrop Hospital, including the outpatient Wound Healing Center clinic.

Patients will be compensated for participation in the trial. Patients will receive one \$25 gift card for each study visit (1 – 12), as well as a \$50 gift card for both the Long-Term Follow-Up visit at Week 26 and the Final Study visit at Week 52.

5.4 PARTICIPANT WITHDRAWAL OR TERMINATION

5.4.1 REASONS FOR WITHDRAWAL OR TERMINATION

A subject may be discontinued from the study at any time if the subject, the Investigator, or the Sponsor feels that it is not in the subject's best interest to continue. The following is a list of *possible* reasons for study discontinuation:

- Screen Failure
- Subject withdrawal of consent
- Subject is not compliant with study procedures
- Adverse Event that, in the opinion of the Investigator, would be in the best interest of the subject to discontinue study participation and/or study intervention
- Protocol violation requiring discontinuation
- Lost to follow-up
- Sponsor request for early termination of study
- Subject death

All subjects are free to withdraw from participation at any time, for any reason, specified or unspecified, and without repercussion.

Reasonable attempts will be made by the Investigator to provide a reason for subject withdrawals. The reason for the subject's withdrawal from the study will be specified in the subject's source documents and the Case Report Form (CRF).

If a subject is withdrawn from treatment due to an AE, the subject will be followed and treated by the Investigator until the abnormal parameter or symptom has resolved or stabilized.

The Investigator must make every effort to contact subjects who are lost to follow-up. Three (3) attempted contacts should be documented by key research personnel in order to consider the participant lost to follow-up. Attempts to contact such subjects must be documented in the patients' records (e.g., times and dates of attempted telephone contact, etc.).

5.4.2 HANDLING OF PARTICIPANT WITHDRAWALS OR TERMINATION

Although subjects may withdraw from the study at any time and for any reason, (or may be withdrawn at the Investigator's discretion), subject withdrawal should be avoided as much as reasonably possible. However, data already accumulated on the patient will be utilized in the final analysis.

Subjects who prematurely discontinue are not to be replaced. For subjects considered lost to follow-up, the CRFs must be completed up to the last visit performed.

5.5 PREMATURE TERMINATION OR SUSPENSION OF STUDY

This study may be temporarily suspended or prematurely terminated if there is sufficient reasonable cause. Written notification, documenting the reason for study suspension or termination, will be provided by the suspending or terminating party to the Investigator, the Sponsor and the Institutional Review Board (IRB), as appropriate. If the study is prematurely terminated or suspended, the Investigator will promptly inform the IRB and will provide the reason(s) for the termination or suspension.

Circumstances that may warrant termination or suspension include, but are not limited to:

- Determination of unexpected, significant, or unacceptable risk to participants
- Demonstration of efficacy that would warrant stopping
- Insufficient compliance to protocol requirements
- Data that are not sufficiently complete and/or evaluable
- Determination of futility

Study may resume once concerns about safety, protocol compliance, and/or data quality are addressed and satisfy the Sponsor and/or the IRB.

6. STUDY AGENT

6.1 STUDY DEVICE DESCRIPTION

MicroMatrix®

MicroMatrix® is composed of a porcine-derived extracellular matrix known as urinary bladder matrix and is intended for the management of topical wounds including: partial and full-thickness wounds, pressure ulcers, venous ulcers, diabetic ulcers, chronic vascular ulcers, tunneled/undermined wounds, surgical wounds (donor sites/grafts, post-Mohs surgery, post-laser surgery, podiatric, wound dehiscence), trauma wounds (abrasions, lacerations, second-degree burns, skin tears) and draining wounds. The device is intended for one-time use.

The devices are supplied in a particle form in masses up to 1000mg, and packaged in a glass vial and a peel-open pouch.

Refer to Instructions for Use for further details.

Cytal® Wound Matrix 1-Layer

Cytal® Wound Matrix 1-Layer is composed of a porcine-derived extracellular matrix also known as urinary bladder matrix. The device is intended for the management of wounds including: partial and full-thickness wounds, pressure ulcers, venous ulcers, diabetic ulcers, chronic vascular ulcers, tunneled/undermined wounds, surgical wounds (donor sites/grafts, post-Mohs surgery, post-laser surgery, podiatric, wound dehiscence), trauma wounds (abrasions, lacerations, second-degree burns, skin tears) and draining wounds. The device is intended for one time use.

The devices are supplied in a sheet configuration in sizes up to 10 cm x 15 cm and packaged in double peel-open pouches.

Refer to Instructions for Use for further details.

6.1.1 ACQUISITION AND ACCOUNTABILITY

The Sponsor (or designee) will ship Cytal® Wound Matrix 1-Layer and MicroMatrix® to the investigational site. The initial study product shipment will be shipped after site activation (i.e., when all required regulatory documentation has been received by the Sponsor and a contract has been executed). Subsequent study product shipments will be made after the site requests for resupply.

Upon receipt of the Cytal® Wound Matrix 1-Layer and MicroMatrix®, an inventory check must be performed against the device receipt log, filled out and signed by the person accepting the shipment. It is important that the designated study staff counts and verifies that the shipment contains all the items noted in the shipment inventory. Any damaged or unusable study devices in a given shipment will be documented in the study files. The Investigator must notify the study Sponsor of any damaged or unusable study devices that were supplied to the Investigator's site.

Regular study device reconciliation will be performed to document device assignment and use. This reconciliation will be logged on the Device Accountability Log and signed and dated by the PI.

6.1.2 PRODUCT STORAGE

MicroMatrix® and Cytal® Wound Matrix 1-Layer should be stored at room temperature in a clean, dry environment, in the unopened and undamaged package. The products should be protected from freezing temperatures, excessive heat, and high humidity.

6.1.3 RETURN OR DESTRUCTION OF STUDY DEVICE

All unused Cytal® Wound Matrix 1-Layer and MicroMatrix® will be returned to the Sponsor at the time of the study Close Out Visit (COV). A detailed Device Accountability Log of the returned study product(s) will be provided to the Sponsor at the end of the study.

7. STUDY PROCEDURES AND SCHEDULE

7.1 STANDARD OF CARE

7.1.1 STANDARD OF CARE DEFINITION

1. No concurrent use of tissue engineered materials (e.g. Apligraf®, Dermagraft®) or other scaffold materials (e.g. Oasis®) at initial treatment or during the 12 week treatment phase.
2. Compression therapy for venous patients, unless contraindicated.
3. Offloading of pressure ulcers and diabetic ulcers as indicated.
4. Negative pressure wound therapy for deep wounds as indicated.
5. Hyperbaric oxygen therapy as indicated.
6. Visual Analog Pain Scale (SOC at each study visit).
7. If signs and symptoms indicate a likely infection, the study product will not be placed, and the wound will be managed per investigator discretion for resolution of infection.
 - a. This includes but is not limited to: topical antimicrobials, systemic antibiotics and debridement in the operating room.

7.2 STUDY SCHEDULE

7.2.1 SCREENING VISIT

(MUST OCCUR WITHIN 7 DAYS OF THE TREATMENT VISIT)

The Screening Visit may be combined with the Treatment Visit, as long as all eligibility criteria have been confirmed prior to treatment.

1. Evaluation for potential eligibility for study inclusion.
2. Obtain informed consent from the potential subject or Legally Authorized Representative.
3. Assign a unique subject identification number (SID). SIDs will be assigned in consecutive order and will not be re-used in the case of Screen Failures.

4. Perform physical examination, wound SOC activities, and review medical, surgical, and medication histories.
5. Perform a pregnancy test for females of reproductive potential.
6. Collect demographic data including: date of birth, gender, race, ethnicity, alcohol use and tobacco use.
7. Collect employment and ambulatory status.
8. Quality of Life Assessments (Katz ADL, W-QoL, VAS).
9. Full wound evaluation and wound management as appropriate.
 - a. Wound photos to include one zoomed out photo with at least one anatomical landmark, at least one zoomed in photo before debridement, at least one zoomed in photo after debridement and at least one zoomed in photo after product application(if applied). All photos taken in accordance with standardized wound care photography protocols.

7.2.2 TREATMENT VISIT (STUDY DAY #0)

1. Ensure subject remains eligible prior to study device application.
2. Document laboratory results and ABI (as required) for lower extremity wounds. Required labs include Hgb A1C (for diabetic subjects), pre-albumin and albumin.
3. Confirm negative pregnancy test for females of reproductive potential prior to initial device application.
4. Document and update changes to concomitant medication log and medical history.
5. Record AEs as reported by participant or observed by Investigator.
6. Perform wound SOC and application of product(s).
7. Document updates and/or changes to Employment and/or Ambulatory status.
8. Wound biopsy prior to product application for pathological evaluation.
9. Full wound evaluation and wound management as appropriate.
10. Wound photos to include one zoomed in photo before debridement, at least one zoomed in photo after debridement and at least one zoomed in photo after product application(if applied). All photos taken in accordance with standardized wound care photography protocols.

7.2.3 REGULAR STUDY VISITS #1-12 AS INDICATED (VISITS ARE SEQUENTIAL AND CONTIGUOUS, BASED OFF OF TREATMENT VISIT)

For All Follow-Up Visits:

1. Full wound evaluation and wound management as appropriate.
 - a. Wound photos to include one zoomed in photo before debridement, at least one zoomed in photo after debridement and at least one zoomed in photo after product application(if applied). All photos taken in accordance with standardized wound care photography protocols.

2. Study device application (up to a maximum of 10 applications between Weekly Follow-up Visit 1 - 12, unscheduled visits and the Initial Device Application at the Treatment Visit) as needed.
3. Assessment of target wound related Adverse Events.
4. Document and update changes to concomitant medication log and medical history
5. Document updates and/or changes to Employment and/or Ambulatory status.
6. Perform delayed wound healing labs & procedures (PRN, as determined by the Investigator).
7. Perform closure and recurrence assessment.

For Follow-Up Visit 6 & 12 ONLY (Wound SOC, FUV activities above, PLUS the following):

1. Document updates and/or changes to Employment and/or Ambulatory status.
2. Document laboratory results and ABI (as required) for lower extremity wounds. Required labs include Hgb A1C (for diabetic subjects), pre-albumin and albumin.
3. Quality of Life Assessments (Katz ADL, W-QoL, VAS).

Biopsy and Pathology (Follow-Up Visits):

For normally healing wounds there will be wound biopsies taken at the following intervals. Each will include IHC staining for macrophage phenotype and quantitative analysis.

1. Biopsy at Initial treatment visit before product application
2. Visit 1 (approximately 7 days post-initial treatment) biopsy required, before debridement and product application, if either is performed
3. A third and final biopsy, when normal healing progress is being made to characterize the normal healing trajectory, but prior to complete epithelization. Timing of biopsy is at the treating Physician's discretion but must be recorded in the database.

For wounds which, in the view of the Investigator, appear to not be progressing to full wound healing, or are stalled in progress, there will be additional wound biopsies taken at the following intervals. Each will include IHC staining for macrophage phenotype and quantitative analysis.

1. Biopsy at Initial treatment visit before product application
2. Visit 1 (approximately 7 days post-initial treatment) biopsy required, before debridement and product application, if either is performed
3. Visit 4 biopsy required, before debridement and product application, if either is performed.
4. A fourth and final biopsy at ~ 70-90% wound closure.

7.2.4 UNSCHEDULED VISIT (RECORD DATE OF VISIT)

Unscheduled visits may occur at any time after the informed consent form is signed until the Final Study Visit occurs. All activities listed below must be conducted on the same calendar day as applicable for that visit, and the visit must be related to the targeted study wound.

1. Document reason for the unscheduled visit.
2. Document and update changes to concomitant medication log and medical history.
3. Perform a physical examination and wound SOC.
4. Record AEs as reported by participant or observed by Investigator.
5. Perform closure and recurrence assessment.
6. Full wound evaluation and wound management as appropriate.
 - a. Wound photos to include one zoomed in photo before debridement, at least one zoomed in photo after debridement. All photos taken in accordance with standardized wound care photography protocols.
7. Perform delayed wound healing labs & procedures. Labs include Hgb A1C (for diabetic subjects), pre-albumin and albumin, as applicable.

7.2.5 LONG-TERM FOLLOW UP VISIT & FINAL STUDY VISIT

(LTFU AT 26 WEEKS [182 DAYS] AND FSV AT 52 WEEKS [365 DAYS] FROM TREATMENT VISIT, ± 14 DAYS)

The following activities are required for the Long-Term Follow-Up Study Visit and the Final Study Visit:

1. Record any changes to employment and ambulatory status.
2. Document and update changes to concomitant medication log and medical history.
3. Record AEs as reported by participant or observed by Investigator.
4. Quality of Life Assessments (Katz ADL, W-QoL, VAS).
5. Perform a physical examination and wound SOC.
6. Perform delayed wound healing labs & procedures (PRN, as determined by the Investigator).
7. Collect updates to tobacco use.
8. Document laboratory results and ABI (as required) for lower extremity wounds (PRN at these visits, not required).
9. Perform closure and recurrence assessment.
10. Full wound evaluation and wound management.
 - a. Wound photos to include one zoomed in photo before debridement, at least one zoomed in photo after debridement (if performed). All photos taken in accordance with standardized wound care photography protocols.

7.3 CONCOMITANT MEDICATIONS, TREATMENTS, AND PROCEDURES

Concomitant prescription medications taken during study participation will be recorded on the case report forms (CRFs). For this protocol, a prescription medication is defined as a medication that can be prescribed only by a properly authorized/licensed clinician. Medications to be reported in the CRF are those related to the study condition as well as any steroids, antibiotics, anti-hypertensives, pain medications, or nutritional supplements (including TPN).

8. ASSESSMENT OF SAFETY

8.1 SPECIFICATION OF SAFETY PARAMETERS

8.1.1 DEFINITION OF ADVERSE EVENTS (AE)

Target wound related Adverse Events (AEs) will be captured from the time of initial treatment. An AE is defined as follows:

- Any adverse change in the subject's medical status when compared with the subject's baseline condition, whether or not the event is related to the device or a procedure; or
- An exacerbation (either in frequency or severity) in a subject's pre-existing condition.

Known sequelae, judged by the Investigator to be associated with target wound procedures (e.g., pain or bleeding associated with debridement) and/or the course of normal wound healing (e.g., slough or mild exudate) should not be recorded as an AE unless: 1) an additional treatment/procedure is required (e.g., use of a concomitant medication); or 2) the frequency, severity and/or duration deviates from the expected course. These include but are not limited to:

- Infection/sepsis
- Worsening of wound bed/failure to heal
- Increased chronic inflammation
- Allergic reaction
- Unexplained fever or chills
- Death
- Neurologic symptoms such as light headedness, headache
- Gastrointestinal symptoms including nausea and vomiting
- Pain

In some cases, an increase in wound size may be documented as an AE. This determination will be made using the following thresholds for overall change in wound size (**from baseline post-debridement measurement**):

- 0-25% - Does not require AE reporting
- 25-50% - Physician discretion – potential opportunity for further investigation of size changes.
- 50%+ - Must be reported as an AE.

The AE will be noted as “resolved” upon $\geq 10\%$ reduction (from largest wound size) maintained for 2 consecutive weeks.

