8.3 TIME PERIOD AND FREQUENCY FOR EVENT ASSESSMENT AND FOLLOW-UP

The occurrence of an AE or SAE may come to the attention of study personnel during study visits or upon review by a study monitor. All AEs (per Investigator discretion) that are possibly impactful to the development or healing of the target wound will be captured on the appropriate CRF. Information to be collected includes event description, date of onset, clinician's assessment of severity, relationship to study products (assessed only by those with the training and authority to make a diagnosis), and time of resolution/stabilization of the event. All AEs will be followed to adequate resolution.

Any medical condition that is present at the time that the participant is screened will be considered as baseline and not reported as an AE. However, if the study participant's condition deteriorates at any time during the study, it will be recorded as an AE.

Changes in the severity of an AE will be documented to allow an assessment of the duration of the event at each level of severity to be performed. AEs characterized as intermittent require documentation of onset and duration of each episode.

The PI will record all reportable events with start dates occurring any time following initial device application through the last day of study participation. At each study visit, the Investigator will inquire about the occurrence of AE/SAEs since the last visit. Events will be followed for outcome information until resolution or stabilization.

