10.1.1 SAFETY ANALYSES

Safety will be assessed by wound examination, clinical laboratory tests and collection of AEs as outlined in the Schedule of Events. All summaries of AEs will be based on treatment-emergent AEs and presented using the incidence and a tabulation of the number of events. The number and percentage of subjects experiencing AEs will be summarized by system organ class and description. Summaries by maximum severity and relationship to the study treatment will also be provided. SAEs and AEs leading to discontinuation from the study will be presented by system organ class and preferred term.

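### A wound-enlargement adverse event can be recorded as resolved while the wound still meets the section 8.1.1 mandatory-reporting threshold

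*Combined protocol and SAP*

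**What the plan says.** Section 8.1.1 sets three bands for enlargement of the study wound, all measured "from baseline post-debridement measurement":

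- "0-25% - Does not require AE reporting"
- "25-50% - Physician discretion"
- "50%+ - Must be reported as an AE"

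The same section then closes the event on a different reference. It is noted as resolved after a fall of at least 10%, described as a "reduction (from largest wound size) maintained for 2 consecutive weeks".

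Three other places use these records:

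- Section 8.3 collects the time at which each event resolved or stabilised, and intends that duration can be assessed by severity level. It adds: "Events will be followed for outcome information until resolution or stabilization".
- Section 10.1.1 summarises adverse events "presented using the incidence and a tabulation of the number of events", and also by number and percentage of subjects.
- Secondary endpoint 4 (section 4.1.2) counts wound-related adverse events through week 12.

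**The concern.** Onset is defined against baseline and resolution against the peak. The larger the peak, the further above baseline the wound may still be when the event is closed. Above a certain peak, one measurement satisfies both the resolution rule and the mandatory-reporting rule.

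Two things are at stake. First, the recorded outcome and resolution date can describe an event as over while the wound is still in the range that made it reportable. Second, site staff who see the wound at the next visit have no instruction. They could leave it under the closed event, or they could read the mandatory line as requiring a fresh report. The tabulated number of events depends on which they do.

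**Working it through.** The documents give no derived figure on this point, so there is none to reproduce. The check is direct arithmetic on the section 8.1.1 rules.

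**Inputs (all from section 8.1.1).** Mandatory reporting: size ratio to baseline of 1.50 or more, with exactly +50% taken as mandatory. Discretionary band: ratio 1.25 to 1.50. Resolution: a fall of at least 10% from the largest size, held for two consecutive weeks.

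**Step 1: size at which closure is first allowed.** Let P be the largest size divided by baseline size. Closure is allowed once the ratio is at or below 0.90 × P for the two weeks. No further fall is required.

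**Step 2: when closure overlaps mandatory reporting.** The wound can still be at or above the mandatory line at closure if 0.90 × P ≥ 1.50, that is, P ≥ 1.50 / 0.90 = 1.667, a peak of +66.7%.

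**Step 3: size at earliest closure, and the fall needed to come down to +50%.** The last column is 1 − 1.50 / P.

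| Peak above baseline | Earliest closure, 0.90 × P − 1 | Still at or above +50%? | Fall from peak needed to reach +50% |
|---|---|---|---|
| +50% | +35% | No | 0.0% |
| +60% | +44% | No | 6.2% |
| +66.7% | +50% | Yes, at the line | 10.0% |
| +80% | +62% | Yes | 16.7% |
| +100% | +80% | Yes | 25.0% |
| +150% | +125% | Yes | 40.0% |
| +200% | +170% | Yes | 50.0% |

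A fixed 10% fall coincides with the mandatory line only at a peak of +66.7%.

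**Step 4: alternative reading.** If the 10% means percentage points of baseline size, the condition is P − 0.10 ≥ 1.50, so the overlap starts at P = 1.60, a peak of +60%. The overlap exists on either reading.

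**Step 5: does another section cure it?** Sections 8.3 and 8.4.1 ask that events be followed to adequate resolution but do not define it, so the specific rule in 8.1.1 governs. No section says how a wound still at or above +50% after closure is to be recorded or counted.

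**The case against.** The strongest reply is that the bands are entry criteria and the 10% rule is an exit criterion, and the two need not share a reference. A 10% fall held for two weeks may be meant to show that enlargement has reversed, and section 8.3 already accepts stabilisation as an end point for follow-up. That is a fair account of a possible purpose, but the protocol does not state it. The label used is resolution, and the result is an event closed while "Must be reported as an AE" still applies to the wound.

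The rest of the reply limits the consequences, and most of it stands. A reader might infer any of the following, and the documents do not support them:

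- *That events are lost or hidden from the counts.* An enlargement that reached +50% has been reported and counted; a resolution date does not remove it. The number and percentage of subjects with an event cannot change, because the subject is already counted.
- *That double counting is built in.* No section tells sites to re-report a shrinking wound. One event with a resolution date is a natural reading. The defect is that the plan leaves the choice open.
- *That a planned duration analysis is biased.* Section 10.1.1 plans no duration or time-to-resolution table. The effect is on the date and outcome recorded under section 8.3.
- *That observation of the wound stops.* The Schedule of Events keeps wound evaluation and planimetry weekly to week 12 whatever the event status, and section 10.1 analyses wound size weekly. Adverse events are also recorded at weeks 26 and 52.
- *That closing at +35% is itself an error.* Peaks from +50% to just under +66.7% can close only below the mandatory line. Nothing in the documents requires a return to the no-report band.

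**Conclusion.** The inconsistency is real and nothing elsewhere in the protocol removes it. For peaks of +66.7% or more (+60% on the percentage-point reading), section 8.1.1 allows an event to be recorded as resolved while the wound still meets the section's own mandatory-reporting criterion. The recorded outcome and resolution date are then inconsistent with the reporting rule, and the event tally in section 10.1.1 and secondary endpoint 4 is open to two interpretations.

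Severity is minor. Subject-level incidence is unaffected, no counted event disappears, and weekly planimetry to week 12 keeps persisting enlargement visible. How many events are touched is unknown, because the documents do not say how often wounds are expected to reach such peaks. The conclusion rests on taking the 8.1.1 resolution rule literally, as the operative definition for this type of event.

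**What to change.** Reconcile the reporting and resolution rules in section 8.1.1, and carry the result into the adverse event form guidance:

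- State that a wound-enlargement event is not recorded as resolved while the wound still meets the mandatory-reporting criterion.
- Have the sponsor and investigator define the exact resolution criterion, including what applies once the wound is below the mandatory line, and keep a confirmation period. Leaving the mandatory band should not be enough by default: a wound peaking at +52% could then close at +49%, a fall of only 1 − 1.49 / 1.52 = 2.0%, which is looser than the present rule.
- State that enlargement persisting after a fall from the peak is the same event and is counted once.

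The cost is a sentence or two of protocol text and matching form guidance. The downside is that some events will show longer durations or remain ongoing.
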